### **3.3 Subject Enrollment and Randomization**

Study participants will be recruited from each site's current and actively managed dialysis population. ESRD patients on a three times weekly hemodialysis regimen will be identified through regular monthly rounding visits by the site PI / Delegated Staff and through interactions with the dialysis unit nursing staff. Patients with a known history of dialysis-associated atrial fibrillation will be sought out for participation in the study. Site PIs will attempt to enroll at least 25% of their patients with a known history of post-dialysis intermittent (but not chronic) atrial fibrillation. Prospective patients will be approached by the site PI or designated clinical research staff to obtain written informed consent before any study-specific screening procedures commence. A log of all patients who entered pre-study screening will be maintained by the site research team.

Patients who meet all inclusion and none of the exclusion criteria will be randomized in a 1:1 ratio to one of two treatment sequences, consistent with a two-period cross-over design. Central randomization via an interactive response technology (IRT) will be utilized; refer to [Section 3.5](#) for details. Randomization codes will be assigned strictly sequentially as patients become eligible for randomization.

A total of 88 patients are planned to be randomized, accounting for an anticipated 10% drop-out rate. Patients who discontinue or are withdrawn from the study post-randomization WILL NOT be replaced (i.e., their randomization code cannot be reused).

### **3.4 Procedures for Handling Incorrectly Enrolled or Randomized Subjects**

Patients who fail to meet the eligibility criteria should not, under any circumstances, be enrolled or receive study medication. There can be no exceptions to this rule. Patients who are enrolled, but subsequently found not to meet all the eligibility criteria must not be randomized or initiated on treatment and must be withdrawn from the study.

Where a subject does not meet all the eligibility criteria but is randomized in error, or incorrectly started on treatment, the PI should inform the Sponsor immediately, and a discussion should occur between the Sponsor and the PI regarding whether to continue or discontinue the patient from treatment. The Sponsor must ensure all decisions are appropriately documented.

### **3.5 Methods for Assigning Treatment Groups**

The study sponsor (NephroNet) will be responsible for preparing the randomization scheme. Permuted block randomization using 2x2 Latin Squares will be applied to ensure a balanced assignment (1:1 ratio) to the two treatment sequences in the study.

Patients who meet all inclusion and none of the exclusion criteria will be randomized to one of two treatment sequences, consistent with a two-period cross-over design:

- Sequence **A**: standard 2.0 K+/2.5 Ca++ dialysate with no Lokelma supplementation for two (2) months, followed by a cross-over to experimental 3.0 K+/2.5 Ca++ dialysate with Lokelma supplementation (on off-dialysis days) for two (2) months;

Or

- Sequence **B**: experimental 3.0 K+/2.5 Ca++ dialysate with Lokelma supplementation (on off-dialysis days) for two (2) months, followed by standard 2.0 K+/2.5 Ca++ dialysate with no Lokelma supplementation for two (2) months.

Central randomization via an interactive response technology (IRT) will be utilized. Randomization codes will be assigned strictly sequentially as patients become eligible for randomization. Randomization will occur by the site PI (or qualified designee) contacting the IRT and obtaining the randomization code and associated treatment sequence for each eligible patient. The original randomization notification will be filed as part of the source documents.

Sites are expected to randomize approximately nine (9) patients on average (no minimum or maximum number of enrolled patients will be specified).

### **3.6 Methods for ensuring blinding**

Not applicable; this is an open label study.

### **3.7 Methods for unblinding**

Not applicable; this is an open label study.

### **3.8 Restrictions**

Apart from the limitations described in the exclusion criteria (see [Section 3.2](#)), there will be no restrictions affecting patients' daily life activities associated with participation in the study.

### **3.9 Discontinuation of Investigational Product**

Patients may be discontinued from investigational product (IP) in the following situations:

- Patient decision. The participant is at any time free to discontinue treatment, without prejudice to further treatment;
- Incorrectly randomized participant where violation of the inclusion/exclusion criteria would put the participant at undue risk;
- Adverse event for which the investigator judges continued treatment may put the participant at undue risk;
- Pregnancy;
- Development of any of the following study-specific criteria for discontinuation:
  - Permanent atrial fibrillation, as determined by echocardiogram or cardiology assessment;

- Requiring for permanent placement of a cardiac pacemaker or AICD;
  - Refractory hyperkalemia ( $K^+ > 6.5$  mEq/L) while on 15 grams 4 days per week of Lokelma;
  - Hypokalemic event (defined as pre-dialysis  $K^+$  level of  $< 3.5$  mEq/L): Patients experiencing a minimum of two (2) hypokalemic events while taking Lokelma will have their Lokelma adjusted or discontinued at the discretion of the site PI;
  - Renal transplant.
- Severe non-compliance with the study protocol.

Note: patients wishing to remain in the study on treatment despite developing an adverse event may do so at the site PI's discretion, unless they remain hyperkalemic with  $K^+ > 6.5$  mEq/L after a long inter-dialytic interval (LIDI) for two (2) consecutive weeks.

Regardless of the reason for discontinuation, all reasons for discontinuation of study treatment must be documented in the electronic case report form (eCRF).

If the patient is discontinued from investigational product, the scheduled study visits, data collection and procedures should continue according to the study protocol until study completion, unless the patient withdraws consent for any further study procedures and follow-up. The approach taken should be documented in the eCRF.

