## **5.3 Safety Protocols**

### **5.3.1 Safety Protocol for Patients with Piccolo POCT-Confirmed Hypokalemia or Hyperkalemia**

Hyperkalaemia will be defined as a  $K^+ \geq 7.0$  mEq/L and measured using Piccolo POCT technology in pre-dialysis obtained after the long dialysis “weekend”. Unless clinically unstable, patients with hyperkalaemia will be dialyzed and managed according to the judgment of the Site PI. Dose adjustments of Lokelma will be with each patient prior to discharge.

Hypokalemia is defined as pre-dialysis  $K^+$  level of  $< 3.5$  mEq/L. Patients experiencing a minimum of two (2) hypokalemic events while taking Lokelma will have their Lokelma adjusted or discontinued at the discretion of the site PI.

Patients with clinically significant cardiac arrhythmias including bradycardia, ventricular tachycardia, and asystole that are recognized by the dialysis staff during an individual dialysis session will be managed according to site unit protocols and include necessary resuscitation and transfer to the nearest emergency department.

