## 7.2 Dose and Treatment Regimens

### 7.2.1 Dosing Regimen

Patients will take Lokelma supplementation on off-dialysis days (4 days/week) while receiving hemodialysis with 3.0 K+/2.5 Ca++ mEq dialysate bath (8-week treatment phase):

- Patients on a Monday-Wednesday-Friday dialysis schedule will take the study drug on Tuesday, Thursday, Saturday, and Sunday
- Patients on a Tuesday-Thursday-Saturday dialysis schedule will take the study drug on Monday, Wednesday, Friday, and Sunday.

The individual starting dose will be 5.0 grams (4 days/week), and will be titrated weekly in 5.0 gram increments up to a maximum of 15.0 grams (4 days/week) to maintain K+ within the desired target range (between 4.0 and 5.5 mEq/L):

- Patients who fail to achieve a pre-dialysis K+ of  $\leq 5.5$  mEq/L after one week of 5.0 grams Lokelma will be treated with 10.0 grams on off-dialysis days for an additional 7 days.
- Patients failing to achieve a pre-dialysis K+ of  $\leq 5.5$  mEq/L after one week of 10.0 grams Lokelma will have their study drug dose increased to 15.0 grams.
- Patients failing to achieve the target K+ after a 7-day course of 15.0 grams Lokelma on off-dialysis days will be considered a treatment failure and withdrawn from the study.

Potassium levels will be regularly monitored throughout the 8-week treatment phase, and the study drug dose adjusted based on the potassium levels (i.e., increased [up to a maximum of 15.0 grams/day] if potassium is  $>5.5$  mEq/L, or decreased if potassium is  $<4.0$  mEq/L).

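### Sections 3.9 and 7.2.1 give unreconciled instructions for high pre-dialysis potassium on Lokelma: stop against step up below 15 g, and above 6.5 against above 5.5 at 15 g

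*Protocol*

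**What the plan says.** Four rules act on a high pre-dialysis K+ while a patient is on the 3.0 K+ bath with Lokelma.

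- **Section 7.2.1, titration.** If K+ is not at or below 5.5 mEq/L after a week on 5 g, the patient "will be treated with 10.0 grams on off-dialysis days for an additional 7 days". The same test after a week on 10 g leads to 15 g. Neither step has an upper potassium limit. A patient who has not reached target after 7 days on 15 g is a treatment failure and leaves the study.
- **Section 3.9, bullet.** The list opens with "Patients may be discontinued from investigational product (IP) in the following situations". One item is refractory hyperkalemia, given as K+ above 6.5 mEq/L "while on 15 grams 4 days per week of Lokelma". How many values are needed, and when they are taken, is not stated.
- **Section 3.9, note.** It begins "patients wishing to remain in the study on treatment despite developing an adverse event may do so at the site PI's discretion", and then makes an exception for patients who stay hyperkalemic with K+ above 6.5 "mEq/L after a long inter-dialytic interval (LIDI) for two (2) consecutive weeks". No dose is stated.
- **Section 5.3.1, safety protocol.** Hyperkalaemia is K+ at or above 7.0 mEq/L on the point-of-care sample taken before the first session that follows the long interval. For a stable patient the instruction is that "patients with hyperkalaemia will be dialyzed and managed according to the judgment of the Site PI", and the Lokelma dose is adjusted. No discontinuation is attached.

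**The concern.** A site holding one potassium result should be able to tell from the protocol whether the patient steps up, stops the drug or leaves the study. Here the answer can depend on which section the site opens. These are patient-safety instructions, and section 6.10 sets up no study committee to settle differences between sites: site investigators decide, and meet the coordinating investigator quarterly.

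There is also a statistical side. Lokelma is given only with the 3.0 K+ bath, so any inconsistency in titrating or stopping it falls on one treatment of the cross-over. It affects experimental exposure and, where the outcome is withdrawal from the study, the loop-recorder data that can still be collected. Values near the cut-offs are foreseeable: inclusion criterion 4 admits screening K+ up to 6.5 mEq/L on the post-weekend sample, and section 1.2 says that patients with persistently high K+ are not likely to tolerate the higher bath.

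**Working it through.** No figure in the plan has to be reproduced. The check sets the rules side by side and applies each to illustrative post-weekend values.

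| Rule | K+ (mEq/L) | Values needed | Dose condition | Applies to | Consequence |
|---|---|---|---|---|---|
| 7.2.1 step-up | above 5.5 | one weekly value | 5 g or 10 g | all on Lokelma | next dose |
| 7.2.1 failure | target not reached (read as above 5.5) | after 7 days | 15 g | all on Lokelma | withdrawn from the study |
| 3.9 bullet | above 6.5 | not stated | 15 g | all on Lokelma | drug may be stopped; visits continue |
| 3.9 note | above 6.5 | two consecutive weeks | not stated | patients with an adverse event who wish to stay on treatment | may not stay on treatment |
| 5.3.1 | 7.0 or more | one value | none | all | investigator manages; dose adjusted |

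**Case 1: a patient with an adverse event, K+ 6.8 after each of a week on 5 g, a week on 10 g and a week on 15 g.**

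- Week 1 (5 g): 7.2.1 gives 10 g, since 6.8 > 5.5. The bullet is not met (dose below 15 g), nor the note (one week only), nor 5.3.1 (6.8 < 7.0). No conflict.
- Week 2 (10 g): 7.2.1 gives 15 g. The note's two weeks are complete, so the patient may not stay on treatment. The bullet and 5.3.1 are still not met. The step-up and the note give opposite instructions, and no section ranks them.
- Week 3 (15 g): 7.2.1 withdraws the patient from the study. The 3.9 bullet, if one value is enough, says only that the drug may be stopped, and section 3.9 then keeps visits and data collection going. 5.3.1 is still not met.

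Without an adverse event the note does not apply, and weeks 1 and 2 raise no conflict.

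**Case 2: K+ 6.0 after 7 days on 15 g.** 7.2.1 is met (6.0 > 5.5) and the patient leaves the study. The 3.9 bullet and note are not met (6.0 < 6.5), nor is 5.3.1 (6.0 < 7.0). The same holds for every value above 5.5 up to 6.5, a band of 6.5 − 5.5 = 1.0 mEq/L. The order is also inverted: the heavier, mandatory consequence sits at the lower potassium cut-off, and the permissive one at the higher.

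**Terminology.** A value of 6.6 to 6.9 is called hyperkalemic in section 3.9 but falls short of hyperkalaemia in section 5.3.1. No stopping decision turns on this.

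**The case against.** A reader might infer that the protocol contains three competing stopping triggers. It does not. Section 5.3.1 governs same-day handling and stops nobody, and an acute-management cut-off may differ from a discontinuation cut-off without contradiction. The 3.9 list is permissive, and section 3.9.1 allows a restart at the investigator's discretion.

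A reader might also take the 3.9 bullet to need only one value and the note to hold at any dose. Both are readings of silence. *Refractory* can as well suggest persistence, and the note simply gives no dose. Nor is the note a free-standing stop rule: it limits discretion for patients with an adverse event. Under section 6.4.6 a worsened protocol-mandated laboratory value is an adverse event only if it meets a seriousness criterion or is the reason for stopping treatment. A high K+ alone will often not bring the note into play.

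At 15 g one could harmonise the sections by taking 7.2.1 to govern the first week on that dose and the 3.9 bullet to govern a later rise. The protocol does not say so. That reading would also leave a later value between 5.5 and 6.5 on the maximum dose without a stated outcome.

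These points narrow the finding. They do not remove the unranked pair below 15 g or the different cut-offs at 15 g.

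**Conclusion.** The point holds in limited form. Two contradictions need reconciling: the 3.9 note against the 7.2.1 step-up for a patient with an adverse event below 15 g, and the 3.9 cut-off of 6.5 against the 7.2.1 target of 5.5 at 15 g. The use of hyperkalemia for two cut-offs is a matter of wording.

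The number of patients affected cannot be taken from the documents. They give no distribution of K+ on the 3.0 K+ bath under titration and no adverse-event rate. Assumed weekly values that ignore titration, the 15 g condition and the adverse-event condition would show how far the cut-offs lie apart, not how many patients are handled inconsistently.

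A reader might go further and conclude that the atrial fibrillation and potassium comparisons are made site-dependent. The documents do not support that as a general claim: patients taken off the drug under 3.9 continue visits, and the full analysis set is analysed as randomized. The exposure that remains is narrower. Where a site applies 7.2.1 and withdraws the patient, later recordings are lost, only as a result of experimental treatment, and section 8.5.2 makes no allowance for missing values in the primary analysis. The conclusion rests on reading the 7.2.1 target as its stated range of 4.0 to 5.5, with failure here meaning above 5.5.

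**What to change.** The sponsor should reconcile the 3.9 bullet, the 3.9 note and section 7.2.1 in one amendment that:

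1. uses consistent conditions on threshold, number of values and dose for the hyperkalemia that ends treatment;
2. states which rule governs when the 7.2.1 step-up and a 3.9 stopping rule are both met;
3. states the outcome for values above 5.5 up to 6.5 on 15 g, so that both sections give the same one;
4. uses a distinct term in section 5.3.1, or aligns its definition with section 3.9.

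The clinical team chooses the thresholds and the order of the rules; no view is taken here on which is right. The cost is a short protocol amendment and a site memo, with no new procedures and no additional patients.

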### **3.9.1 Procedures for Discontinuation of a Patient from Investigational Product**

At any time, patients are free to discontinue investigational product or withdraw from the study (i.e., investigational product and assessments – see [Section 3.10](#)), without prejudice to further treatment. Patients deciding to discontinue the investigational product will be asked to: (i) provide the reason(s) for discontinuation, including the development of any adverse event(s) contributing to their decision; (ii) return to the clinic for the remaining study visit(s) and assessment(s); and (iii) return all unused study drug to the site. Adverse events will be followed up, as described in [Section 6](#).

The investigational product (Lokelma) can be discontinued abruptly (without the need for gradual treatment stepdown or tapering). Patients may be allowed to re-start the investigational product at the discretion of the site PI.

Patient withdrawal from study is described in [Section 3.10](#).

## **3.10 Criteria for Withdrawal**

Patients can decide to be discontinued from both investigational product **and** further study procedures/visits at any time (withdrawal of consent).

### **3.10.1 Screen failures**

Screening failures are patients who do not fulfil the eligibility criteria for the study, and therefore must not be randomized. These patients should have the reason for study withdrawal recorded as 'Incorrect Enrollment' (i.e., patient does not meet the required inclusion/exclusion criteria). This reason for study withdrawal is only valid for screen failures (not randomized patients).

### **3.10.2 Withdrawal of the informed consent**

Patients are free to withdraw from the study at any time (investigational product and assessments), without prejudice to further treatment.

A patient who withdraws consent will always be asked about the reason(s) and the presence of any AE. Regardless of the reason for withdrawal, all data available for the patient at the time of discontinuation of follow-up must be recorded in the eCRF.

If a patient withdraws from participation in the study, his/her randomization code cannot be reused. Withdrawn randomized patients will not be replaced.

Patients who withdraw consent prior to completion of the study, will have the option to either keep the ILR device implanted or have their ILR device removed by the affiliated electrophysiology cardiologist.

### **3.11 Discontinuation of the study**

The study may be stopped if, in the judgment of the Sponsor, trial participants are placed at undue risk because of clinically significant findings that:

- meet individual stopping criteria or are otherwise considered significant
- are assessed as causally related to study drug
- are not considered to be consistent with continuation of the study.
- Unscheduled ECG will be performed if a patient develops a suspected arrhythmia since date from the loop recorded will not be evaluated simultaneously. ECG will also be measured if S-K < 3.0. If an absolute QTc >550ms, or an increase in QTc interval > 60ms from baseline to more than 500ms is reached the subject will immediately receive appropriate medical intervention and be discontinued from the study drug treatment. The QTcF algorithm (QT interval corrected by the Fridericia method) is recommended. All patients meeting the QTc>500ms criterion will immediately have potassium assessed, if not already done within 1 hour of performing the ECG.

Regardless of the reason for termination, all participant data available at the time of study stopping must be recorded in the eCRF. For patients still in the study at the time of study discontinuation, the reasons for discontinuation should be documented as “Study termination by the Sponsor”.

In terminating the study, the Sponsor will ensure that adequate consideration is given to the protection of the patients’ interests.

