### **5.3.2 Safety Protocol for Patients with Intra-Dialytic Arrhythmias**

Patients developing clinically apparent dialysis-associated arrhythmia including atrial fibrillation with or without with rapid ventricular response (RVR), atrial tachycardia (defined as sustained pulse  $>130$  bpm), bradycardia (defined a symptomatic pulse of  $< 40$  bpm) will be sent to the nearest emergency department for treatment at the discretion of the PI. All such events will be marked by the LINQ marking device.

If a complete metabolic panel is performed as standard of care, the results will be recorded in the patient’s source chart and electronic data capture system (EDC).

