## **6.1 Definition of Adverse Events**

An adverse event is the development of an undesirable medical condition or the deterioration of a pre-existing medical condition following or during exposure to a pharmaceutical product, whether or not considered causally related to the product. An undesirable medical condition can be symptoms (e.g., nausea, chest pain), signs (e.g., tachycardia, enlarged liver) or the abnormal results of an investigation (e.g., laboratory findings, electrocardiogram). In clinical studies, an AE can include an undesirable medical condition occurring at any time, including run-in or washout periods, even if no study treatment has been administered.

The term AE is used to include both serious and non-serious AEs.

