#### **6.4.6 Adverse events based on examinations and tests**

The results from protocol-mandated laboratory tests and vital signs measurements will be summarized in the clinical study report. Deterioration from baseline in protocol-mandated

laboratory values or vital signs should therefore only be reported as AEs if they fulfil any of the SAE criteria or are the reason for discontinuation of study treatment.

If deterioration in a laboratory value/vital sign is associated with clinical signs and symptoms, the sign or symptom will be reported as an AE and the associated laboratory result/vital sign will be considered as additional information. Wherever possible the reporting Investigator should use the clinical, rather than the laboratory term (e.g., anaemia versus low hemoglobin value). In the absence of clinical signs or symptoms, clinically relevant deteriorations in non-mandated parameters should be reported as AE(s).

Any new or worsened (compared to baseline) clinically relevant abnormal physical examination findings should be reported as an AE.

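### The only on-study QTc stopping rule for study drug sits in section 3.11, on terminating the study, while sections 3.9 and 3.9.1 leave continuation and restart to the site PI

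*Protocol*

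**What the plan says.** Protocol section 3.11 sets out when the sponsor may stop the study. Its last bullet turns to the individual patient. It calls for an unscheduled ECG if an arrhythmia is suspected or if S-K is below 3.0. If QTc exceeds 550 ms, or rises by more than 60 ms from baseline to above 500 ms, "the subject will immediately receive appropriate medical intervention and be discontinued from the study drug treatment".

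Section 3.9 covers stopping study drug in a patient. Its list opens permissively: "Patients may be discontinued from investigational product (IP) in the following situations". The study-specific criteria are permanent atrial fibrillation, need for a pacemaker or AICD, refractory hyperkalemia, hypokalemic events and renal transplant. A note adds that "patients wishing to remain in the study on treatment despite developing an adverse event may do so at the site" PI's discretion, unless K+ stays above 6.5 mEq/L after the long interval for two consecutive weeks.

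Section 3.9.1 says: "Patients may be allowed to re-start the investigational product at the discretion of the site PI". Section 6.9 sends the reader to 3.9 for the events that require permanent discontinuation.

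**The concern.** A rule that obliges a site to stop study drug in a patient belongs where sites look when deciding about that patient. Here it stands in a list of reasons for ending the whole trial. The section written for the patient-level decision leaves it out and contains a general permission to continue.

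A site working from 3.9 and the safety protocols in 5.3 could miss the unscheduled ECG, or treat a compulsory stop as a matter of judgment. Section 1.3 names treatment-associated hypokalemia with worsening arrhythmia as a risk of taking part, and this bullet is the protocol's only on-study QTc safeguard. Section 6.10 sets up no study committees, so applying the rule rests with the sites.

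**Working it through.** No arithmetic applies beyond counting. The check sets every part of the protocol on QTc, ECG or stopping study drug side by side.

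1. **Is 3.11 the only on-study QTc rule?** Yes. The other QT text is in exclusion criteria 1 and 20 (section 3.2), which act at entry only. Section 5.2.3.1 describes the screening ECG. Sections 5.3 and 6.9 contain no QTc rule.

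2. **Is it a patient-level rule?** Yes. The first three bullets of 3.11 complete the sentence about findings that may stop the study. The last bullet does not; it instructs the site on one subject.

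3. **Does 3.9 contain it?** No. QTc accounts for 0 of the 5 study-specific criteria. The general adverse-event criterion in 3.9 could lead to a stop, but it depends on the investigator's judgment, whereas 3.11 does not.

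4. **Does the 3.9 note reach a QTc event?** On the text, yes. Section 6.1 includes among adverse events "the abnormal results of an investigation (e.g., laboratory findings, electrocardiogram". The reporting limit in 6.4.6 says that deteriorations in protocol-mandated "laboratory values or vital signs should therefore only be reported as AEs if they fulfil any of the SAE criteria" or lead to discontinuation; it does not mention ECG. The note has 1 exception, persistent hyperkalemia, and QTc is not in it.

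5. **Take one patient:** QTc above 550 ms during the Lokelma period, wishing to continue. Section 3.11 requires a stop. The 3.9 note leaves the decision to the site PI. Neither section cites the other, and no order of precedence is stated.

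6. **What happens after a stop?** Section 3.11 does not say whether it is permanent. The restart sentence in 3.9.1 carries no QTc condition.

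7. **Do the cross-references lead to 3.11?** No. Section 6.9 points to 3.9. The opening of section 6 points to 4.2.2, 5.1.2 and 5.3.2 for serious arrhythmias. The safety protocols for the two ECG triggers are 5.3.1 (low potassium) and 5.3.2 (arrhythmia), and 0 of these 2 has an ECG step. In 5.3.1, patients with at least two hypokalemic events "will have their Lokelma adjusted or discontinued at the discretion of the site PI". In 5.3.2, patients with clinically apparent arrhythmia "will be sent to the nearest emergency department for treatment at the discretion of the PI", and the event is marked on the device.

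**The case against.** The strongest reply is that nothing is missing. Section 3.11 is binding and gives triggers, thresholds, a recommended correction formula, a mandatory consequence and a potassium check. The 3.9 note permits continuation without requiring it, so a PI who stops the drug under 3.11 breaches nothing. A specific compulsory rule normally prevails over a general permission. Firmer instructions stand outside 3.9 elsewhere too: 6.8.1 on pregnancy and 7.2.1 on treatment failure at 15 g. This stands in part, and it rules out the stronger reading that the two sections cannot both be obeyed. It does not settle the matter, because the protocol never states the precedence, and that reading helps only someone who has found the bullet in 3.11.

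The restart sentence in 3.9.1 follows text on patients who themselves decide to stop, so applying it to a QTc stop is an inference. But its wording is general and does not exclude such a stop.

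Two further inferences are tempting and not supported:

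- A reader might see a contradiction between an ECG at S-K below 3.0 (3.11) and action on Lokelma after two pre-dialysis values below 3.5 mEq/L (5.3.1). These are different, compatible actions, and 6.9 and 7.2.1 already lower the dose when K+ falls below 4.0 mEq/L.
- A reader might take the screening-only wording in 5.2.3.1 to forbid later ECGs. It describes the scheduled eligibility ECG of 4.1.7; those in 3.11 are unscheduled.

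The stakes are also lower than the lack of committees suggests. Potassium is measured weekly before and near the end of dialysis. Loop-recorder data are reviewed weekly, with PI contact for clinically significant arrhythmias. The PIs meet quarterly on safety, and sites are trained on the protocol. None of these measures QTc, but they address the hypokalemia and arrhythmia risk.

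**Conclusion.** Wrong as written: an inconsistent safety rule, of minor severity. Sections 3.9 and 3.9.1, as worded, allow continuation or restart in a patient for whom 3.11 orders a stop, and the protocol's own cross-references lead sites away from 3.11. The inconsistency is unresolved, but a site that applies 3.11 complies.

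The conclusion assumes that QTc prolongation beyond the thresholds counts as an adverse event, which 6.1 supports. The drug stop matters only while Lokelma is being taken. The protocol gives no rate of QTc events, so the number of patients affected cannot be estimated. Sample size and the primary analysis are unaffected.

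**What to change.** - Move the QTc rule and its two ECG triggers from 3.11 to 3.9, as a criterion at which study drug must be discontinued, kept apart from the permissive list.
- Extend the exception in the 3.9 note to patients who meet the QTc criterion.
- In 3.9.1, either exclude QTc stops from restart or state the QTc condition under which restart is allowed.
- Cite the rule in 5.3.1 (ECG at S-K below 3.0) and 5.3.2 (ECG for suspected arrhythmia). Cite it in 6.9 only once permanence is settled, since 6.9 concerns permanent stops.
- Optionally, say in 5.2.3.1 and Table 1 that the screening-only wording refers to the scheduled eligibility ECG.

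Thresholds and procedures stay as they are. The cost is protocol wording and one sponsor decision on restart. No new procedure is needed, because 3.11 already requires these ECGs.
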